**Covariate Selection:**

We expect, due to randomization and sufficiently large sample size, that demographic, clinical characteristic, and outcome variables at baseline in the four conditions will not be significantly different. However, we will perform tests for differences (imbalances) on demographic (e.g. age, race, gender) and other potential confounder variables across the four groups. Imbalances may occur in spite of the randomization procedure. If by chance there are important variables significantly out of balance we will add them as covariates in the models.

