Covariate Selection: We expect, due to randomization and sufficiently large sample size, that demographic, clinical characteristic, and outcome variables at baseline in the four conditions will not be significantly different. However, we will perform tests for differences (imbalances) on demographic (e.g. age, race, gender) and other potential confounder variables across the four groups. Imbalances may occur in spite of the randomization procedure. If there are important variables significantly out of balance we will add them as covariates in the models. In addition, all models will include covariates indicating whether the participants are using HAART.

Missing Data: Missing data can arise from active refusal and from participants who cannot be located. Attrition will be carefully monitored. We will attempt to assess all participants at follow up regardless of whether they engage with smoking cessation services during the study (intent-to-treat). To assess the potential confounding effects of missing data, we will compare the baseline characteristics of participants who do and do not complete the 12- and 36-week assessments. If we find significant differences between dropouts and completers and differential attrition, we will include any potential confounding variables as covariates. If a subject fails to complete interim visits, we will attempt to re-engage him/her for the 36 week visit in order to ascertain the primary abstinence endpoint. If a subject refuses to be contacted or otherwise loses contact with the investigators, we will censor data at the point of loss and the subject will be considered non-abstinent. In addition, the investigative team will agree by consensus on a set of rules to guide the imputation of missing data.

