values in the various study scales. If necessary, we will conduct a sensitivity analysis to investigate how estimates/results change over a range of several plausible assumptions regarding the missing mechanism together with multiple imputations to most accurately capture existent random variability. Multiple Comparisons: We will use the sequential Bonferroni-type procedure for dependent hypothesis tests⁹⁹ to control the false discovery rate (the expected (or on average) proportion of falsely rejected hypotheses) at 5%. Primary Aims: We will use separate logistic regression models (SAS, 9.3: Proc Logistic) at each post baseline time point to assess the main effects of bupropion vs. placebo (Drug) and PSF vs. SOC (Beh) on smoking cessation. In addition, we will assess any covariates that were identified above. The test of the hypotheses will be the test of whether the coefficients for the main effects are significantly different from 0 based on the likelihood ratio test. To assess if the combination of bupropion and PSF is significantly more effective than either of the treatments alone, we will create an indicator variable for these 3 conditions with the combined treatment as the reference. The analysis will proceed as described above.

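### Apart from HAART use, and that only in the SAP, covariates for the primary models are chosen by significance tests instead of being fixed in advance

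*SAP*

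**What the plan says.** Both documents expect that "demographic, clinical characteristic, and outcome variables at baseline in the four conditions will not be significantly different", but still plan significance tests on demographic and "other potential confounder variables across the four groups".

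- **Imbalance trigger.** SAP, Covariate Selection: "If there are important variables significantly out of balance we will add them as covariates in the models". Protocol, Sample Size and Data Analysis, Covariate Selection: "If by chance there are important variables significantly out of balance we will add them as covariates in the models".
- **Dropout trigger, SAP only.** SAP, Missing Data: "If we find significant differences between dropouts and completers and differential attrition, we will include any potential confounding variables as covariates".
- **Fixed covariate, SAP only.** "all models will include covariates indicating whether the participants are using HAART".
- **Link to the primary analysis.** SAP, Primary Aims: "In addition, we will assess any covariates that were identified above". The protocol's Primary Aims paragraph makes the same link.

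Age, race and gender are examples and not a closed list. The protocol describes randomisation in permuted blocks of varying size and names no stratification factor. Baseline smoking severity appears only as a possible moderator; it could enter the primary models only by failing a balance or dropout test.

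**The concern.** A primary model should be one that can be written out in full before the data are seen. Here the covariates depend on observed imbalance, on observed dropout, and on two undefined judgements: which variables are important, and which are potential confounders. The two documents also imply different models.

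Under randomisation, a significant baseline difference is a chance event and says nothing about whether the variable predicts quitting. Adjustment in logistic regression gains power only when the covariate is prognostic. A rule that picks by imbalance will usually leave the useful variable out. At stake are a reported odds ratio whose covariates were chosen after the fact, and a modest amount of power.

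**Working it through.** **Inputs from the documents.** 300 participants, 1:1:1:1, so 75 per cell; 20% attrition; abstinence 10% v 25% (bupropion) and 7% v 20% (PSF); two-sided alpha .05; claimed power above 80%.

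**Step 1. The plan's own figure.** Retained: 300 × 0.8 / 4 = 60 per cell, 120 per condition. With pooled variance under the null, power = Φ{[(p2 − p1) − 1.96·√(2p̄(1 − p̄)/n)] / √([p1(1 − p1) + p2(1 − p2)]/n)}.
- 10% v 25%: (0.15 − 1.96 × 0.0491) / 0.0481 = 1.12, power 86.9%.
- 7% v 20%: (0.13 − 1.96 × 0.0441) / 0.0433 = 1.01, power 84.3%.

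The claim reproduces.

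**Step 2. How often chance alone changes the model.** Assume each imbalance test uses .05 (no level is stated) and k independent variables. P(at least one flagged) = 1 − 0.95^k: 22.6% for k = 5, 40.1% for 10, 64.2% for 20. Any one prognostic variable is flagged about 5% of the time.

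**Step 3. Effect on power and type I error.** Simulation, 10,000 trials per scenario, all 300 analysed, 20% lost at random and scored non-abstinent. Model: drug, behavioural arm, HAART, plus covariates; likelihood ratio test of drug. Assumed: no behavioural effect; 90% HAART use, not prognostic; ten independent normal baseline variables, one of them prognostic. Every flagged variable is entered, which is an upper bound because importance is undefined. The third effect size is smaller than the plan's and is added for range.

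Power (%), rule v pre-specified covariate:

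| Covariate OR per SD | 10% v 25% | 7% v 20% | 10% v 20% |
|---|---|---|---|
| 1 (not prognostic) | 86.3 v 86.5 | 85.1 v 85.3 | 58.1 v 58.4 |
| 1.5 | 85.7 v 86.3 | 84.7 v 85.2 | 57.9 v 58.8 |
| 2 | 86.4 v 88.0 | 84.2 v 85.7 | 58.2 v 60.6 |
| 3 | 86.2 v 90.0 | 85.6 v 88.4 | 58.5 v 63.5 |

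- Gains from pre-specifying are 0.5 to 0.9, 1.5 to 2.4 and 2.8 to 5.0 points at OR 1.5, 2 and 3, and within 0.3 points if the covariate is not prognostic.
- A model with HAART only is within 0.3 points of the rule throughout (for example 86.0 v 86.2% at 10% v 25%, OR 3).
- The prognostic variable was selected in 4.4 to 5.4% of trials.
- With no drug effect (17.5% in both arms), rejection was 5.1 to 5.7% for all approaches.
- At 10% v 25% the rule changed the significance decision in about 1% of trials.

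**Step 4. Four-group test against the drug comparison.** Aims 1 and 2 each compare 150 with 150, but the balance test has three degrees of freedom. P(χ² on 3 df > 7.81, given |z| > 1.96 on the drug contrast) = 0.37, so 63% of drug-arm differences significant at .05 go unflagged. That is .05 × .63 = 3.1% of trials per variable. The missed ones are borderline. Since √7.81 = 2.80, every |z| above 2.80 is flagged, which is 2.80 × √(2/150) = 0.32 SD. The median missed |z| is 2.15, about 0.25 SD.

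**Step 5. What adjustment does to the odds ratio.** Scoring 20% as non-abstinent turns 10% v 25% into 8% v 20%. Unadjusted OR = (0.20/0.80) / (0.08/0.92) = 2.88. Conditional on a covariate with OR 1.5, 2 or 3 per SD, the same rates give 2.93, 3.05 or 3.35.

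**The case against.** The strongest reply is that the rule does almost no harm. Type I error holds, decisions change in about 1% of trials, and the median odds ratio under the rule stays flat (2.93, 2.95, 2.93 as the covariate strengthens). The power at issue rests on covariate strengths that no document supplies, and nothing in the documents says baseline expired CO predicts quitting. All of this stands, and it limits the point to a model that is not fixed and some power that may be forgone.

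A reader might go further in four ways that the documents or the arithmetic do not support.

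- **That the rule inflates false positives.** Overall it does not. In trials where a prognostic drug-arm imbalance is missed, the rate is 6.7, 7.2 or 9.0% at OR 1.5, 2 or 3. That event occurs in 3.1% of trials per variable, so the effect on overall error is about 0.03 to 0.11 points.
- **That missing 63% of imbalances defeats the rule.** Large imbalances are always caught. A four-arm check also suits Aim 3, which compares individual arms, and the protocol's model with a drug-by-behaviour interaction.
- **That the dropout trigger creates or cures attrition bias.** For someone who is lost, "the subject will be considered non-abstinent"; a baseline covariate does not undo that. With no drug effect and an assumed loss of 10% v 30%, the drug odds ratio is 0.80 without and 0.78 with the dropout-related covariate. An unrelated fixed covariate also leaves it at 0.80.
- **That very light smokers are known to be eligible.** The one-cigarette threshold is in the advertisement text; the eligibility checklist is an attachment that was not available.

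**Conclusion.** The point holds in a limited form. Apart from HAART use in the SAP, neither document fixes a covariate for the primary models; the choice waits on significance tests and undefined judgements. The imbalance rule behaves like no adjustment and leaves overall type I error essentially unchanged. Against one pre-specified prognostic covariate it gives up about 0.5 to 1, 1.5 to 2.5 and 3 to 5 points of power at a covariate OR of 1.5, 2 and 3 per SD, and nothing if the covariate is not prognostic. Those strengths, the .05 test level and the ten candidate variables are assumptions. The mismatch between a four-group test and two-group aims is secondary, because the differences it misses are borderline. It should be changed because the change is cheap and lets the primary model be stated in advance, not because the plan's conclusions are at serious risk.

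**What to change.** Before unblinding, replace both significance-test triggers in the primary models with one covariate set, worded identically in the two Covariate Selection sections:

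1. HAART use, as the SAP already says, omitted only if it does not vary.
2. One named baseline smoking-severity measure already collected. Expired CO at the Baseline visit is an example, on a scale defined at zero such as log(CO + 1), since log CO fails at 0 ppm.

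Label the odds ratio as conditional on these covariates and add an unadjusted sensitivity analysis. Report the baseline and dropout comparisons descriptively. Use dropout-related variables only in the missing-data sensitivity analysis that the SAP already mentions.

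**Cost.** Wording changes in two documents and one extra analysis, with no new data, visits or participants. The adjusted odds ratio will differ from the unadjusted one for the same rates (for example 2.93 to 3.35 against 2.88). If the chosen measure does not predict quitting, there is no power gain. Bias from scoring lost participants as non-abstinent remains and needs its own treatment.

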**1 \* Describe the purpose, specific aims, or objectives of this research. State the hypothesis to be tested:**

Primary Aim 1: Compare bupropion therapy to placebo on rates of 7-day point prevalence abstinence (PPA) at 36 weeks in smokers with HIV/AIDS. We hypothesize that rates of smoking abstinence at week 36 will be higher in those treated with bupropion compared to placebo.

Primary Aim 2: Compare Positively Smoke Free to low intensity, brief counseling on rates of 7-day PPA at 36 weeks in smokers with HIV/AIDS. We hypothesize that rates of smoking abstinence at week 36 will be higher in those treated with Positively Smoke Free compared to brief counseling.

Primary Aim 3: Compare Positively Smoke Free + bupropion to the other two study conditions outlined above on rates of 7-day PPA in smokers with HIV/AIDS at 36 weeks. We hypothesize the effect of Positively Smoke Free with bupropion therapy is greater than the effect of Positively Smoke Free or bupropion therapy alone.

Secondary Aim: Estimate the organizational costs of implementing Positively Smoke Free, bupropion or both. All cost estimates will be appropriately time-discounted and inflation-adjusted. The planned assessment will yield rigorously obtained approximations of total implementation costs at a new site of care.

Exploratory Aim: Explore whether the effect of PSF compared to brief counseling with bupropion is greater than the effect of PSF without bupropion.

Given the critical need for information about the up-front expenses required to implement smoking cessation services in Kenya, we plan to conduct an implementation costs assessment to provide rigorously obtained approximations of total implementation costs of each intervention tested in this trial.

Sub Study:

AIM 1: Develop, culturally adapt and update the PSF intervention in the main study to include educational material about the cancer risk associated with tobacco and alcohol use.

AIM 2: Preliminarily determine the extent the updated PSF syllabus changes awareness of the link between alcohol and tobacco use and cancer.

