Female participants who have the potential to become pregnant will have a pregnancy test during the evaluation phase and approximately monthly during the study (while taking study medication). They will be asked to use acceptable method of contraception during the medication phase of the study (week 1-12). Participants will sign a contraception consent to confirm their agreement (In the baseline packet). Condoms will also be provided at research appointments.

Baseline Interview:

Participants will also complete a series of assessment questionnaires (baseline interview). Vital signs will also be recorded. Only those continuing to meet full inclusion criteria and do not meet exclusion criteria will proceed to randomization and remain in the study. The list of assessments to be completed are located in the study schedule in the Additional Documents section.

Randomization

Study participants who are deemed eligible for the study will complete baseline testing and will then be randomized 1:1:1:1 to four study conditions: (1) Bupropion + PSF; (2) Bupropion + SOC; (3) Placebo + PSF; (4) Placebo + SOC. Participants will be randomly assigned to one of the four conditions using permuted blocks which will randomly vary in size. The research pharmacy will be notified of the drug randomization (Bupropion or placebo). All raters, investigators, and other staff will be blind to treatment assignment except for the dispensing pharmacist. Separate emergency unblinding envelopes for each participant will be kept in a locked cabinet at the dispensing pharmacy in the case of a medical emergency. All participants who are randomized will be taught the correct use of the study medication, and assisted in setting a quit date with the instruction to quit on approximately Day 8 (beginning of Week 2) following one week of medication.

Medication Intervention:

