*** Full Title: Optimizing smoking cessation interventions for PLWH in Nairobi, Kenya**

STATISTICAL ANALYSIS PLAN

Power Calculations: With a total of 300 participants and an estimated 20% attrition, we expect 60 participants per cell in the factorial design. This will provide a total of 120 participants per main effect condition (Drug or Psychosocial Intervention). All power analyses were conducted with a two tailed alpha of .05 and powerset to .80. With the expected sample and the anticipated retention rate, the study's 2 main effects((1) bupropion vs. placebo; (2) PSF versus SOC) are each powered to detect a Cohen's h of from .28 to .36 (small effect)98. In addition, we will be able to determine if there is a significant additive effect (i.e. whether the combination of bupropion and PSF is significantly better than either treatment alone). For this comparison we have sufficient power to detect an effect size of $h = .39 - .49$ (small to medium effect). The evaluation of the exploratory interaction Aim is a possible but not necessary benefit of a factorial design that could determine whether the combination of the two treatments provides more than a simple additive effect. The interaction effect is powered to detect a Cohen's d of .9 (large effect)98. Power was calculated using the PASS software. (Version 13, Logistic Regression Procedure.)

Overview of Analytic Methods: The primary study analyses will adopt an intent-to-treat strategy. Data will be screened for errors using frequency and contingency tables and univariate and bivariate plots before formal analysis. These plots and summaries will allow us to be cognizant of data distribution characteristics before building regression models. To assess indication of self-selection bias, we will compare the demographic characteristics of the participants that agreed to participate in the study to those who were approached, but were not interested in participating.

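### Primary Aim 3 (combination better than either treatment alone) has no stated success rule, and the stated 80% power does not hold if both comparisons must succeed

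*SAP*

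**What the plan says.** The protocol (Justification, Objective, & Research Design, item 1) makes this a primary aim, with abstinence assessed at week 36, and words the hypothesis as follows: "We hypothesize the effect of Positively Smoke Free with bupropion therapy is greater than the effect of Positively Smoke Free or bupropion therapy alone". The SAP, under Power Calculations, describes the same question as "whether the combination of bupropion and PSF is significantly better than either treatment alone".

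Under Primary Aims, the SAP first describes logistic regressions in which the drug and behavioural coefficients are tested against zero by likelihood ratio. For Aim 3 it adds that "we will create an indicator variable for these 3 conditions with the combined treatment as the reference", and refers back to that preceding analysis for the test. It gives no degrees of freedom, no direction, and no statement of which results count as success.

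For power, the SAP says "All power analyses were conducted with a two tailed alpha of .05 and powerset to .80" and "With a total of 300 participants and an estimated 20% attrition, we expect 60 participants per cell in the factorial design". It gives a detectable effect for Aim 3 of Cohen's h from .39 to .49.

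The protocol (Sample Size and Data Analysis, item 2) describes a different primary model: a generalized linear mixed model in GLIMMIX with drug, behavioural and interaction terms. Simple effects are examined only if the interaction is significant.

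**The concern.** Showing that a combination beats each of two components requires two results: it beats PSF alone, and it beats bupropion alone. A likelihood ratio test of the whole three-level variable asks something else, namely whether the three arms differ in any way. It has no direction, and it will often reject when the combination matches the better component and the other component is weak. Testing the two coefficients one at a time estimates the right contrasts, but without a rule that both must succeed, a single significant contrast could be reported as meeting the aim.

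At stake is whether two treatments are worth delivering instead of one. The secondary aim costs PSF, bupropion or both, so an unsupported claim for the combination would bear directly on that choice.

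**Working it through.** **Inputs from the documents.** Allocation is 1:1:1:1 with 300 randomised, so 75 per cell, or 60 after 20% attrition. Alpha is two-sided .05 and power .80. Protocol rates are 10% to 25% for bupropion against placebo and 7% to 20% for PSF against standard of care. The SAP counts participants lost to contact as non-abstinent, so up to 75 per cell could be analysed.

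**Assumed.** No combination rate is given in the documents, so the combination rates below are assumptions. So is a single-treatment rate set at 10%, which is the protocol's placebo rate and means that treatment does nothing.

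**Step 1: the SAP's own effect sizes.** Detectable h = (z(.975) + z(.80)) × √(1/n₁ + 1/n₂), with 1.960 + 0.842 = 2.802.
- Main effects, 120 per arm: 2.802 × √(2/120) = .362. This reproduces the upper end of .36.
- Aim 3, pairwise, 60 per cell: 2.802 × √(2/60) = .511. Power from Φ(h√(n/2) − 1.96) is 57% at h = .39 and 77% at h = .49.
- Aim 3, pairwise, 75 per cell: 2.802 × √(2/75) = .457. Power is 67% and 85%.
- Aim 3, joint 2-df test with equal single arms: noncentrality 9.63 is needed for 80% power, and h = √(9.63 / (60 × 2/3)) = .491.
- 60 against 120 at alpha .025: (2.241 + 0.842) × √(1/60 + 1/120) = .487.

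The range .39 to .49 is therefore not reproduced as a pairwise comparison at 60 per cell. Its upper end fits two different calculations, so it does not reveal which test was intended.

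**Step 2: how often Aim 3 could be declared met when the combination adds nothing to its better component.** Each row is 400,000 simulated trials with three binomial arms, no covariates, 60 per cell, and likelihood ratio tests at unadjusted .05.

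| Combination / bupropion alone / PSF alone | Joint 2-df test | At least one contrast favours combination | Both contrasts favour combination |
|---|---|---|---|
| 25 / 25 / 20% | 9.9% | 11.6% | 1.1% |
| 20 / 10 / 20% | 34% | 37% | 2.1% |
| 25 / 25 / 10% | 62% | 61% | 2.5% |

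The first row uses the protocol's planned rates for the two single treatments. The other two assume that one treatment does nothing. At 75 per cell the third row becomes about 72%, 70% and 2.6%.

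**Step 3: power of the claim that needs both contrasts.** Assume both single arms have the same rate p. The combination rate is then sin²(arcsin√p + h/2).

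| Single arms | h | Combination | Joint test, 60 per cell | Both, 60 per cell | Both, 75 per cell |
|---|---|---|---|---|---|
| 20% | .39 | 37.5% | 60% | 42% | 52% |
| 20% | .49 | 42.4% | 81% | 65% | 76% |
| 25% | .39 | 43.3% | 60% | 40% | 52% |
| 25% | .49 | 48.3% | 80% | 64% | 77% |

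The 75-per-cell column assumes that these rates still hold once lost participants are counted as non-abstinent. If that counting lowers the rates, h shrinks as well.

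**The case against.** A reader might infer that the SAP commits to a joint 2-df test and is therefore plainly wrong. The documents do not support that. The back-reference is to a model with two coefficients that answer two separate hypotheses, and those are naturally tested one at a time. Making the combination the reference matters only if individual coefficients are read, because a global likelihood ratio test is the same whichever level is the reference. With that coding the two coefficients are exactly the contrasts the aim needs. Cohen's h is also a two-group measure. Separate testing is at least as natural a reading.

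The large percentages also need care. At 25/25/10% the combination really is better than PSF alone, and most of the 61% is that true difference. The false contrast, combination against bupropion alone, favours the combination in only about 2.6% of trials. The 61% becomes an error rate only if one significant contrast is reported as superiority to both, which the SAP does not say it will do. In plain English, superiority to either treatment alone already suggests both comparisons.

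These points stand, and they limit the finding to an unspecified test and success rule. They do not remove it. The false discovery rate procedure lists no family of tests. If the family were just these two contrasts with the Benjamini–Yekutieli adjustment, at least one would still be rejected in about 45% of trials at 25/25/10% and 6% at 25/25/20%. The procedure cannot turn a test of any difference into a claim about both. The protocol's GLIMMIX model supplies no rule for Aim 3 either.

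**Conclusion.** The concern holds as a gap in specification that has consequences. The SAP fixes neither the test nor the criterion for Aim 3. Two permissible readings, the joint test or one significant coefficient, would let the aim be declared met when the combination only equals one component. It does not follow that the wrong test will be used.

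The size depends on assumed rates. With the single arms at their planned rates and the combination no better than bupropion, the joint test rejects in about 10% of trials. The 34% and 62% figures require one treatment to have no effect. Requiring both contrasts keeps the rate at 1% to 2.5% throughout.

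The power statement is affected on any reading that secures the aim. At the stated h of .39 to .49, with equal single arms, power for both contrasts is about 40–65% at 60 per cell and 52–77% at 75, not 80%. Even one pairwise contrast at 60 per cell needs h of about .51. These figures are unadjusted for covariates and for the false discovery rate procedure. The inputs behind the SAP's h range are not given, so that range cannot be checked fully.

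**What to change.** Amend the SAP's Primary Aims and Power Calculations before analysis:

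- Define Aim 3 by two 1-df contrasts at 36 weeks: combination against PSF alone, and combination against bupropion alone.
- Declare Aim 3 met only if both are significant at two-sided .05 and both favour the combination. Do not use the global three-level test for this aim.
- Report both odds ratios with confidence intervals, whatever the outcome.
- State how Aim 3 enters the false discovery rate family. One option is to enter the larger of the two p-values as its single p-value.
- Restate power for the both-contrasts rule, giving the assumed rates in all three arms and the number analysed per cell.
- Reconcile this with the protocol's GLIMMIX model with the drug-by-behavioural interaction, so that one analysis governs Aim 3.

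No new data are needed. The success rule is one sentence; the power restatement and the reconciliation are short edits. The cost is that the stated power for Aim 3 becomes visibly less favourable, and a true advantage of the combination over only one component would no longer count as meeting the aim.
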